Pressure ulcer assessment ⁶ (digital photograph taking, investigator's photo evaluation) - Ulcer size (Using a scale) - Complete healing status	V ⁷	V	V	V	V	V	V	V	V	V	V	V	V	V	V	V	V	V	V	V	V	V	V	V	V	V

Item	Schedule	Screening		Treatment period																		Closing					
		1*	2*	3	4	5	6	7	8	9	10	11	12	13	14**												
		-14d~0d	1d (±1d)	5d* (±1d)	8d (±1d)	12d* (±1d)	15d (±1d)	19d* (±1d)	22d (±1d)	26d* (±1d)	29d (±1d)	33d* (±1d)	36d (±1d)	40d* (±1d)	43d (±1d)	47d* (±1d)	50d (±1d)	54d* (±1d)	57d (±1d)	61d* (±1d)	64d (±1d)	68d* (±1d)	71d (±1d)	75d* (±1d)	78d (±1d)	82d* (±2d)	85d (±2d)
PUSH		V			V				V				V				V			V							V
Self-dressing training		V		V	V	V	V	V	V	V	V	V	V	V	V	V	V	V	V	V	V	V	V	V	V	V	V
Dressing change frequency review				V	V	V	V	V	V	V	V	V	V	V	V	V	V	V	V	V	V	V	V	V	V	V	V
Infection sign checklist ⁸ (CSSC)		V		V	V	V	V	V	V	V	V	V	V	V	V	V	V	V	V	V	V	V	V	V	V	V	V
Subject diary distribution ⁹		V		V	V	V	V	V	V	V	V	V	V	V	V	V	V	V	V	V	V	V	V	V	V	V	V
Subject diary return				V	V	V	V	V	V	V	V	V	V	V	V	V	V	V	V	V	V	V	V	V	V	V	V
Concomitant medication/treatment review	V	V		V	V	V	V	V	V	V	V	V	V	V	V	V	V	V	V	V	V	V	V	V	V	V	V
Adverse event review		V		V	V	V	V	V	V	V	V	V	V	V	V	V	V	V	V	V	V	V	V	V	V	V	V

* Visit 1 and Visit 2 can take place on the same day.

** Subjects who have complete healing during the study or are withdrawn from the study will have all tests scheduled for V14.

¥ Subject do not make a site visit but perform self-dressing.

† Except for Randomization visit, Home Health Care system through study coordinator will be used for those subjects who aren't able to make a visit during the treatment period. Physical examination and measuring weight may be exempt in case of replacing visit with Home Health Care.

- Blood pressure, pulse, body temperature measurement
- Laboratory tests: If test findings within 2 weeks prior to the consent date are available, they may be used instead of screening findings.
 - Hematology: WBC, RBC, platelet, WBC count, Hb, Hct
 - Blood chemistry: AST, ALT, ALP, creatinine, BUN, total bilirubin, glucose, protein, albumin, gamma GTP, TSH (TSH is conducted at screening only)
- Urine hCG pregnancy test is conducted only in women of child-bearing potential.
- The investigational device is changed twice weekly; additional changes are allowed depending on the pressure ulcer condition, without any limitation to frequency.

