12.1.2 Visit 2 (enrollment, 1d)

Subject enrollment will take place at the second visit, and the following assessment will be conducted.

- ① Conduct the physical examination.
- ② Review the inclusion/exclusion criteria, and subjects who are finally determined eligible will go through the process of randomization.

- ③ Before applying the investigational device, check the infection signs using the CSSC(Clinical Signs and Symptoms Checklist).
- ④ Before applying the investigational device, take a photograph of the study ulcer, investigator will conduct a photo evaluation, and record the pressure ulcer size by a Scale.
- ⑤ After conducting standard dressing, apply the investigational device.
- ⑥ Record the baseline PUSH score.
- ⑦ Review concomitant medication and treatment-emergent adverse events.
- ⑧ Prescribe the investigational devices and train the subject or guardian on the self-dressing method.
- ⑨ Dispense the subject diary to record the frequency of position changes per day (if applicable) and the frequency of additional self-dressing.

12.1.3 Visit 3, 4, 5, 6, 7, 8, 9, 10, 11, 12, 13 (interim visit, 8d, 15d, 22d, 29d, 36d, 43d, 50d, 57d, 64d, 71d, 78d)

The following tests will be conducted at the interim visit. It can be replaced by home health care through coordinator's visit if the subject is not able to visit the institution.

- ① Conduct the physical examination.
- ② As vital signs, measure blood pressure, pulse, and body temperature.
- ③ Measure body weight (only 29d).
- ④ After removing the investigational device, take a photograph of the study ulcer, conduct the investigator's photo evaluation, and record the pressure ulcer size by a Scale and complete healing status.
- ⑤ Check the infection signs using the CSSC (Clinical Signs and Symptoms Checklist).
- ⑥ After conducting standard dressing, apply the investigational device.
- ⑦ After conducting the pressure ulcer assessment, record the PUSH score (15d, 29d, 43d, 57d, 71d).
- ⑧ Review concomitant medication and adverse events (all adverse events, local adverse events at the study ulcer).
- ⑨ Prescribe the investigational devices and train the subject or guardian on the self-dressing method.
- ⑩ At the last visit, investigational devices that have been prescribed but not used are to be returned.
- ⑪ Based on the subject diary, record the frequency of self-dressing beyond once-weekly in the Case Report Form.

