12.2.11 PUSH(Pressure Ulcer Scale for Healing)

From Visit 2 (1d), the PUSH score will be checked at a 2-week interval (15d, 29d, 43d, 57d, 71d, 85d). Using a Version 3.0 PUSH tool, the score will be calculated according to the following criteria, and each sub-score and the total score will be recorded in the Case Report Form.

DIRECTIONS:

Observe and measure the pressure ulcer. Categorize the ulcer with respect to surface area, exudate, and type of wound tissue. Record a sub-score for each of these ulcer characteristics. Add the sub-scores to obtain the total score. A comparison of

Length	0 0 cm ²	1 <0.3 cm ²	2 0.3-0.6 cm ²	3 0.7-1.0 cm ²	4 1.1-2.0 cm ²	5 2.1-3.0 cm ²	
× Width	-	6 3.1-4.0 cm ²	7 4.1-8.0 cm ²	8 8.1-12.0 cm ²	9 12.1-24.0 cm ²	10 >24.0 cm ²	Sub-score
Exudate Amount	0 None	1 Light	2 Moderate	3 Heavy	-	-	Sub-score
Tissue Type	0 Closed	1 Epithelial Tissue	2 Granulation Tissue	3 Slough	4 Necrotic Tissue	-	Sub-score
-	-	-	-	-	-	-	Total Score

total scores measured over time provides an indication of the improvement or deterioration in pressure ulcer healing.

Length × Width: Measure the greatest length (head to toe) and the greatest width (side to side) using a centimeter ruler. Multiply these two measurements (length x width) to obtain an estimate of surface area in square centimeters (cm²). Caveat: Do not guess! Always use a centimeter ruler and always use the same method each time the ulcer is measured.

Exudate Amount: Estimate the amount of exudate (drainage) present after removal of the dressing and before applying any topical agent to the ulcer. Estimate the exudate (drainage) as none, light, moderate, or heavy.

Tissue Type: This refers to the types of tissue that are present in the wound (ulcer) bed. Score as a "4" if there is any necrotic tissue present. Score as a "3" if there is any amount of slough present and necrotic tissue is absent. Score as a "2" if the wound is clean and contains granulation tissue. A superficial wound that is reepithelializing is scored as a "1." When the wound is closed, score as a "0."

- 4 - Necrotic Tissue (Eschar):** black, brown, or tan tissue that adheres firmly to the wound bed or ulcer edges and may be either firmer or softer than surrounding skin.
- 3 - Slough:** yellow or white tissue that adheres to the ulcer bed in strings or thick clumps, or is mucinous.
- 2 - Granulation Tissue:** pink or beefy red tissue with a shiny, moist, granular appearance.

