15.1 General principles of result analysis

Data obtained from subjects in this study will be analyzed as the SS(Safety Set) and the FAS(Full Analysis set).

- 1) In the SS(Safety set), data obtained from subjects who were enrolled in the study, had at least

- 1 application of the study device, and had at least 1 safety assessment will be analyzed.
- 2) In the FAS(Full analysis set), data obtained from subjects who were enrolled in the study, had at least 1 application of the study device and then had at least 1 available endpoints of main interest review will be included in analysis.

Efficacy and demographics will be analyzed using the FAS and safety data will be analyzed using the SS.

For subjects with a missing value during the study or who are withdrawn from the study prior to study completion, efficacy analysis will be conducted by applying the LOCF (Last Observation Carried Forward), only in case such subjects have available endpoints of main interest assessment results after the investigational device application. However, in case of missing values for Other endpoints and safety endpoints, raw data will be used for analysis, without applying LOCF.

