### **Early completion criteria**

Subjects who achieve complete healing\* of the target pressure ulcer will complete the study early. Subjects who can complete the study early will undergo all tests scheduled for the End-of-Study (85d) visit and then complete the study.

(\* Complete healing: Defined as the condition with the epithelial tissue covering 100% of the study ulcer, no abrasion or ulceration, intact dermis and epidermis.)

---

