## (2) Other endpoints

- ① PUSH reduction rate at each time point

$$\text{Reduction rate} = \frac{\text{PUSH score on 1d} - \text{PUSH score at each time point}}{\text{PUSH score on 1d}} \times 100\%$$

- ② Dressing change frequency during the entire study period

: Calculated as the additional dressing frequency beyond twice daily

- ③ Number of subjects with early completion due to complete healing during the study
- ④ Incidence of new infections at the pressure ulcer until Week 12 based on the CSSC

$$\text{Infection incidence} = \frac{\text{Number of subjects with at least 1 new infection}^{**} \text{ until Week 12, after the study device application}}{\text{Total number of subjects}} \times 100\%$$

(\*\* Infection: Presence of 'Purulent exudates' or 2 or more symptoms of the CSSC. However, for subjects with an infection at baseline, it is defined as development of an additional symptom other than those confirmed at baseline or recurrence of baseline-identified symptoms after being completely healed.)

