## **(2) Analysis of other endpoints**

For other endpoints, present the mean, median, min, max and standard deviation for the continuous variable PUSH reduction rate at each time point, and frequency and percentage for categorical variables of Dressing change frequency, Number of subjects with early completion due to complete healing, and Incidence of new infections at the pressure ulcer after investigational device application. t-test and paired t-test will be conducted for PUSH reduction rate while Fisher's exact test will be used to see the difference between Medifoam and Betafoam for Dressing change frequency, Number of subjects with early completion, and Incidence of new infections.

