## 9. Handling Missing Values

---

---

For subjects with a missing value during the study or who are withdrawn from the study prior to study completion, efficacy analysis will be conducted by applying the LOCF (Last observation Carried Forward), only in case such subjects have available endpoints of main interest assessment results after the investigational device application. However, in case of missing values for other endpoints and safety endpoints, raw data will be used for analysis, without applying LOCF.

---

---

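### Interim PUSH rows analysed on raw data omit healed and withdrawn subjects, so Table 0701 compares subgroups selected by outcome; the net direction is unknown

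*SAP*

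**What the plan says.** SAP 7.1 (2) lists "PUSH reduction rate at each time point" among the other endpoints, defined as the percentage fall from the 1d score. SAP 8 adds that "t-test and paired t-test will be conducted for PUSH reduction rate", and Table 0701 prints N, mean, SD, median, range and p-values for each visit.

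For missing values, SAP 9 applies LOCF to the endpoints of main interest and then makes an exception: "However, in case of missing values for other endpoints and safety endpoints, raw data will be used for analysis, without applying LOCF". Protocol 15.1 carries the same sentence.

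On leaving the study, SAP 5 says: "Subjects who can complete the study early will undergo all tests scheduled for the End-of-Study (85d) visit and then complete the study". The footnote to the Protocol's schedule of study activities covers withdrawals as well: "Subjects who have complete healing during the study or are withdrawn from the study will have all tests scheduled for V14". Protocol 12.1.4 defines Visit 14 as either the 85d visit or the early-completion visit of a healed subject, and has the PUSH score recorded there.

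On timing, Protocol 12.2.11 says that from Visit 2 "the PUSH score will be checked at a 2-week interval (15d, 29d, 43d, 57d, 71d, 85d". The Table 0701 shell nevertheless opens with a Visit 3 (8d) row and then runs over Visits 4 to 13.

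**The concern.** A completely healed ulcer has area 0, no exudate and tissue type 0, so its PUSH total is 0 and its reduction is 100%, the highest possible value. The subject leaves at that point, and neither document gives a PUSH value for the interim visits still to come. An interim row that follows some healings therefore holds only subjects not yet healed. Withdrawn subjects drop out of the same rows, and the discontinuation criteria in Protocol 14.1 include worsening of the ulcer, so some of those absences are also related to outcome.

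Randomization protects a comparison of all subjects assigned to each arm. It does not protect a comparison of those who have neither healed nor withdrawn by 57d or 71d. The between-arm t-tests, the within-arm paired tests and the plain descriptive means all carry this selection. The printed N shows how many subjects are missing but does not correct for it.

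The plan is also uneven. Ulcer size is a main-interest endpoint and falls under LOCF, so a subject healed at 43d stays at 0 cm² in the 57d and 71d rows of Table 0604 but is absent from the same rows of Table 0701. Length × width is itself a PUSH component. Protocol 5.1 says that a further trial will use this study's result, so the interim PUSH profile may be read for planning.

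**Working it through.** **Inputs from the documents.** 10 subjects per arm, withdrawals not replaced (Protocol 9); PUSH at 1d, 15d, 29d, 43d, 57d, 71d and 85d (12.2.11); PUSH 0 at complete healing; raw data for other endpoints (SAP 9). The documents give no healing rate, withdrawal rate, expected PUSH value or SD, so there is no figure to reproduce and every rate below is an assumption.

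**One arm, one interim row.** Let h be the share healed and gone, w the share withdrawn, u the mean reduction in those still observed, and v the reduction that withdrawn subjects would have shown.

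- Raw row mean = u.
- All-subject mean = 100h + wv + (1 − h − w)u.
- All-subject minus raw = h(100 − u) − w(u − v).

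The first term is the loss from omitting healed subjects and lowers the raw mean. The second is the effect of omitting withdrawn subjects and raises it when v is below u. With n = 10, u = 40 and an assumed v = −20:

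| Healed | Withdrawn | Raw | All subjects | Difference |
|---|---|---|---|---|
| 2 | 0 | 40 | (200 + 320)/10 = 52 | 12 |
| 2 | 1 | 40 | (200 − 20 + 280)/10 = 46 | 6 |
| 2 | 2 | 40 | (200 − 40 + 240)/10 = 40 | 0 |
| 1 | 2 | 40 | (100 − 40 + 280)/10 = 34 | −6 |

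The sign of the net error therefore depends on numbers that the documents do not give.

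**Between arms, no withdrawals.** The raw difference (arm 2 minus arm 1) is understated by h₂(100 − u₂) − h₁(100 − u₁). I took 0 to 5 of 10 healed per arm, u₁ from 30 to 60, and u₂ equal to u₁ or 10 or 20 points higher in the arm that heals more. Negative values mean that the difference is overstated.

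- Equal healing: −10 to 0 points.
- One more healed: −6 to 7.
- Two more healed: −2 to 14.
- Three more healed: 2 to 21.

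The ranking can reverse. With 6 of 10 healed and u = 30 against 2 of 10 healed and u = 40, the raw rows show 30 v 40, while all subjects give 0.6 × 100 + 0.4 × 30 = 72 v 0.2 × 100 + 0.8 × 40 = 52.

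**When it matters, no withdrawals.** In a simulation where PUSH reduction grows linearly, a better device also helps unhealed ulcers, and exit scores are filed only as Visit 14, the 71d arm means fell short by 6.0 to 19.8 points. The 71d difference was understated by 1.0 to 7.8 points when the arms differed and by 0 when they were equal. At 57d the difference was understated by 0.7 to 6.7, at 43d by at most 3.1, and at 29d by about 0. A second simulation, with assumed PUSH losses of 10% v 6% per week and each exit score kept in its own visit row, gave a 71d difference of 3.9 raw against 19.0 with healed subjects counted, a gap of 15.1. The range is therefore model-dependent, and the effect is mainly at 57d and 71d.

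**Scale.** The standard error of a difference is SD × √(2/10): 8.9, 13.4 and 17.9 points for assumed SDs of 20, 30 and 40.

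**The case against.** The strongest objection concerns direction. A reader might infer that Table 0701 understates the arm means, and so hides a device's benefit. The documents do not support that: withdrawn subjects leave the same rows, probably with poor scores, and the table above shows that this can cancel or outweigh the loss of healed subjects. The objection stands in full on direction. It does not remove the selection, because two opposite omissions do not restore the randomized comparison.

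A reader might also infer, from the 8d row in the shell, that off-schedule rows would fill up with 100% exit scores from healed subjects. Protocol 12.1.4 largely answers this: a healed subject's early-completion assessment is Visit 14, and 85d±2d in the shell is best read as the nominal window. The final PUSH row then does contain the healed subjects. What remains is a shell that lists visits at which PUSH is not scheduled, which is a template slip.

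Finally, the stakes are low. PUSH is not a main-interest endpoint, the study is exploratory with 20 subjects, and Protocol 16.2 plans no formal test. Healing is reported directly in Tables 0601, 0602 and 0704, and ulcer area in Tables 0603 and 0604. Most of the modelled errors are below one standard error. All of this stands and limits the severity, but SAP 8 does plan t-tests, and the descriptive means carry the same selection without them.

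**Conclusion.** The point holds and is minor. Under the raw-data rule, healed early completers and withdrawn subjects are absent from later interim PUSH rows, so those rows of Table 0701 compare subgroups selected by outcome. Because a healed subject's exit score belongs to Visit 14, it is also missing from the interim row of the visit at which healing was found.

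Omitting healed subjects alone lowers an arm's mean by h(100 − u), for example by 12 points with 2 of 10 healed and u = 40%. Omitting withdrawn subjects with poor scores works the other way. Net direction and size are unknown, for an arm mean and for the difference between arms. If nobody heals or withdraws before 71d, there is no effect.

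The Visit 14 row is unaffected for healed subjects, and the main-interest endpoints are unaffected. Comparing raw with all-subject means assumes that a healed ulcer stays healed, which the study does not observe after exit.

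**What to change.** In SAP 9 and Protocol 15.1, handle PUSH by the rule already used for ulcer size:

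- A subject who completes early through complete healing counts as PUSH 0 (100% reduction) at the scheduled PUSH visit where healing is found and at every later scheduled PUSH visit.
- A withdrawn subject carries the last observed post-baseline PUSH score.
- Each row shows the number healed and carried and the number withdrawn and carried.
- The raw-data analysis is kept as a sensitivity table.
- Table 0701 is limited to 15d, 29d, 43d, 57d, 71d and 85d/Visit 14.

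Both groups need a rule. Carrying only the healed subjects at 100% can be further from the all-subject mean than raw data: with 2 healed, 2 withdrawn at −20% and u = 40, it gives (200 + 240)/8 = 55, against 40 for all subjects and 40 raw.

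The cost is a few sentences in each document, one derivation step, two counts per row and one extra table. Treatment and visits do not change. The downside is two assumptions that cannot be checked after exit: that healed ulcers stay healed, for up to 11 weeks if healing is found at 8d, and that withdrawn subjects stay at their last score. The first is not trivial, since the CSSC in Protocol 12.2.6 lists breakdown of new epithelium as a sign. The LOCF rule for ulcer size already makes both assumptions, and the raw table shows how much they matter.

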## 10. Midterm Analysis

---

---

The midterm analysis will not be conducted for this study.

---

---

## 11. Others

---

---

### Further Consideration

- In principle, the analysis shall follow the methods presented in Protocol No. BTF16-AP-401 and the general items regarding statistical analysis procedure shall be described.
- For continuous variables, Shapiro-Wilk test with p-value 0.05 will be used for normality test. t-distribution approximation method will be used for Wilcoxon rank sum test.
- Chi-square test will be used on half of Fisher's exact test in case when SAS 9.3 cannot handle the amount of test calculation.

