8.2 Exclusion criteria

- 1) Any study ulcer of the NPUAP Stage I, II or IV
- 2) Diabetic ulcer or Venous ulcer (or stasis ulcer)
- 3) Past history of surgical treatment within 1 year or irradiation at the target pressure ulcer within 1 year
- 4) Hypersensitivity reaction to this product or povidone-iodine
- 5) Hyperthyroidism or thyroid disorder requiring drug treatment
- 6) Signs of a current underlying systemic infection (sepsis/bacterial infection/tuberculosis) or cellulitis or osteomyelitis
- 7) Type 1 diabetes
- 8) Current malnutrition
- 9) Heavy smoker: Current smoking level of ≥ 1 pack (20 cigarettes)/day of tobacco
- 10) Drug or alcohol addiction
- 11) Requirement of immunosuppressants during the study or current chemotherapy or radiotherapy
- 12) Application of other investigational product/medical device within 1 month prior to the

investigational device application (1d)

13) Pregnant or breastfeeding women

14) Other renal, hepatic, neurological, immunological disorder that may interfere with the wound healing process, at the discretion of the investigator

9. Target number of subjects and the rationale

The target number of subject enrollment is 20 subjects, with 10 subjects per group.

This study has a purely explorative goal so that no formal sample size calculation will be conducted but it was planned to enroll 10 subjects per group as the minimum sample size to achieve study objectives from a scientific perspective.

- ✓ Medifoam group: 10 subjects
- ✓ Betafoam group: 10 subjects

Even if a subject is withdrawn from the study, the subject will not be replaced.

10. Study method

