16.2 Assessment criteria and methods

This study is a pilot study with no comparator, so that no formal statistical test will be conducted.

17. Safety assessment methods and criteria, and interpretation methods, including adverse events

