### Analysis of Efficacy Endpoints

#### (1) Analysis of endpoints of main interest

- ① For subjects achieving complete healing within 12 weeks, present frequency and percentage. Fisher's exact test will be performed to compare Medifoam and Betafoam treatment groups.
- ② For the time to 100% complete healing, analyze using the Kaplan-Meier method. Time table for subjects to 100% complete healing will be presented and the survival Plot will be shown as a figure. Subjects not achieving 100% complete healing within 12 weeks will not be considered for evaluation for end point of main interest though ulcer size reduction will be evaluated for those subjects.

- ③ For the pressure ulcer size by each time point, present the mean, median, min, max and standard deviation. t-test will be conducted to compare Medifoam and Betafoam, and paired t-test will be used to see the difference between each post visit and baseline(1d).
- ④ For the pressure ulcer size reduction rate, present the mean, median, min, max and standard deviation. t-test will be conducted to compare Medifoam and Betafoam.
- ⑤ For the analysis for efficacy, conduct sub-analyses by use of topical antibiotics and glucocorticoids for the pressure ulcer during the study. t-test will be performed to compare Medifoam and Betafoam, and paired t-test will be used to see the difference between post visits and baseline(1d).

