Figure 0601 Time to complete healing of ulcer within 12 weeks

[figure not shown]

Table 0603 Pressure ulcer size by each time point and change from 1d (baseline)

Time points		Medifoam	Betafoam	Total	P-value
Visit2(1d)	N	xx	xx	xx	0.xxxx*
	Mean±Std	xx.xx±x.xx	xx.xx±x.xx	xx.xx±x.xx	
	Median	xx.xx	xx.xx	xx.xx	
	Min~Max	xx.xx~xx.xx	xx.xx~xx.xx	xx.xx~xx.xx	
Visit3(8d±1d)	N	xx	xx	xx	0.xxxx*
	Mean±Std	xx.xx±x.xx	xx.xx±x.xx	xx.xx±x.xx	
	Median	xx.xx	xx.xx	xx.xx	
	Min~Max	xx.xx~xx.xx	xx.xx~xx.xx	xx.xx~xx.xx	
Visit4~Visit14	..(Middle Part omitted)..				

Note) \*: t-test, ¥ : Wilcoxon rank sum test

Table 0604 Pressure ulcer size reduction rate based on scale at each time point

Time points		Medifoam	Betafoam	Total	P-value
		n(%)	n(%)	n(%)	
Visit3(8d±1d)	N	xx	xx	xx	0.xxxx*
	Mean±Std	xx.xx±x.xx	xx.xx±x.xx	xx.xx±x.xx	
	Median	xx.xx	xx.xx	xx.xx	
	Min~Max	xx.xx~xx.xx	xx.xx~xx.xx	xx.xx~xx.xx	
	P-value(within)	0.xxxx#			

Visit4~Visit13	..(Middle Part omitted)..				
Visit14(85d±2d)	N	xx	xx	xx	0.xxxx*
	Mean±Std	xx.xx±x.xx	xx.xx±x.xx	xx.xx±x.xx	
	Median	xx.xx	xx.xx	xx.xx	
	Min~Max	xx.xx~xx.xx	xx.xx~xx.xx	xx.xx~xx.xx	
	P-value(within)	0.xxxx#			

Note) \*: t-test, ¥ : Wilcoxon rank sum test #: Paired t-test, \$: Wilcoxon signed rank test

Table 0605 Sub-analysis on Pressure ulcer size reduction rate based on scale at each time point by Use of topical antibiotics

Use of Topical antibiotics	Time points	Medifoam	Betafoam	Total	P-value	
Topical antibiotics used	Visit3(8d±1d)	N	xx	xx	xx	0.xxxx*
		Mean±Std	xx.xx±x.xx	xx.xx±x.xx	xx.xx±x.xx	
		Median	xx.xx	xx.xx	xx.xx	
		Min~Max	xx.xx~xx.xx	xx.xx~xx.xx	xx.xx~xx.xx	
	Visit4~Visit13	..(Middle Part Omitted)..				
	Visit14(85d±2d)	N	xx	xx	xx	0.xxxx*
		Mean±Std	xx.xx±x.xx	xx.xx±x.xx	xx.xx±x.xx	
		Median	xx.xx	xx.xx	xx.xx	
Min~Max		xx.xx~xx.xx	xx.xx~xx.xx	xx.xx~xx.xx		
Topical antibiotics Not used	Visit3(8d±1d)	N	xx	xx	xx	0.xxxx*
		Mean±Std	xx.xx±x.xx	xx.xx±x.xx	xx.xx±x.xx	
		Median	xx.xx	xx.xx	xx.xx	
		Min~Max	xx.xx~xx.xx	xx.xx~xx.xx	xx.xx~xx.xx	
	Visit4~Visit13	..(Middle Part Omitted)..				
	Visit14(85d±2d)	N	xx	xx	xx	0.xxxx*
		Mean±Std	xx.xx±x.xx	xx.xx±x.xx	xx.xx±x.xx	
		Median	xx.xx	xx.xx	xx.xx	
Min~Max		xx.xx~xx.xx	xx.xx~xx.xx	xx.xx~xx.xx		

Note) \*: t-test, ¥ : Wilcoxon rank sum test

Table 0606 Sub-analysis on Pressure ulcer size reduction rate based on scale at each time point by Use of glucocorticoids

Use of glucocorticoids	Time points		Medifoam	Betafoam	Total	P-value
Glucocorticoids used	Visit3(8d±1d)	N	xx	xx	xx	0.xxxx*

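### The SAP fixes a t-approximation for every Wilcoxon rank sum p-value in arms of at most 10, where the exact test is readily available and more accurate

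*SAP*

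**What the plan says.** The SAP's Further Consideration list (section 11) gives two rules for continuous variables: "Shapiro-Wilk test with p-value 0.05 will be used for normality test", and then "t-distribution approximation method will be used for Wilcoxon rank sum test". It offers no exact option, names no minimum group size and does not say whether a continuity correction applies.

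The rank sum test appears as the alternative to the t-test in the table notes ("t-test, ¥ : Wilcoxon rank sum test"). Those notes stand under the main efficacy Tables 0602 to 0606, and under the baseline, PUSH, vital sign and laboratory tables.

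Protocol section 9 sets the group sizes: "The target number of subject enrollment is 20 subjects, with 10 subjects per group", and "Even if a subject is withdrawn from the study, the subject will not be replaced". The arms can therefore only shrink.

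Two parts of the SAP make the groups smaller again. Section 8 leaves subjects who do not heal within 12 weeks out of the time-to-healing evaluation, so Table 0602 compares healers only. The same section asks the analyst to "conduct sub-analyses by use of topical antibiotics and glucocorticoids for the pressure ulcer during the study", which splits the sample in Tables 0605 and 0606. For categorical data the SAP already uses Fisher's exact test, with a computing fallback for that test alone.

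**The concern.** A t-approximation to the rank sum statistic is a convenience for samples too large to enumerate. Here the largest comparison has C(20,10) = 184,756 arrangements, which takes seconds at most. The SAP uses an exact method for the 2 x 2 tables and an approximation for the ranks of the same 20 subjects, and gives no reason.

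Two features of this trial strain the approximation. The groups are small by design. Healed ulcers also share one value (0 cm², 100% reduction), so the size endpoints can be heavily tied. Protocol section 5.1 says a further trial will draw on these results, so the printed p-values may be read closely even though they are descriptive.

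**Working it through.** **Inputs from the documents.** At most 10 per arm, no replacement (Protocol section 9); t-approximation for the rank sum test (SAP section 11). The documents give no power, alpha or p-value for this test, so there is no figure to reproduce.

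**Assumptions.** Two-sided 0.05 is used as a reference level; the SAP states 0.05 only for Shapiro-Wilk. The approximation is taken as z = (|U − mn/2| − c)/√V, referred to t with m + n − 1 df. Both c = 0.5 (continuity correction) and c = 0 are shown. Without ties, V = mn(m + n + 1)/12. With ties, N = m + n and t tied values, V = (mn/12)[(N + 1) − (t³ − t)/(N(N − 1))]. Exact p-values come from full enumeration.

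**1. 10 v 10, no ties.** mn/2 = 50, V = 100 × 21/12 = 175, √V = 13.23, 19 df. For U = 23, z = 26.5/13.23 = 2.003 with the correction and 27/13.23 = 2.041 without.

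| U | Exact p | Printed, c = 0.5 | Printed, c = 0 |
|---|---|---|---|
| 23 | 0.0433 | 0.0596 | 0.0554 |
| 22 | 0.0355 | 0.0514 | 0.0477 |
| 21 | 0.0288 | 0.0443 | 0.0410 |

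The exact test rejects at U ≤ 23 (true size 4.3%). The approximation rejects at U ≤ 21 (2.9%) with the correction, or U ≤ 22 (3.5%) without. U = 22 crosses 0.05 only if the correction is used; U = 23 crosses either way.

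**2. Complete separation (U = 0) in small strata.** Exact p = 2/C(m + n, m). The stratum sizes are assumed, since the documents give none.

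| Sizes | Exact p | z, c = 0.5 | Printed, c = 0.5 | Printed, c = 0 |
|---|---|---|---|---|
| 4 v 4 | 2/70 = 0.029 | 7.5/√12 = 2.165 (7 df) | 0.067 | 0.054 |
| 3 v 5 | 2/56 = 0.036 | 7.0/√11.25 = 2.087 (7 df) | 0.075 | 0.060 |
| 2 v 8 | 2/45 = 0.044 | 7.5/√14.67 = 1.958 (9 df) | 0.082 | 0.066 |

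Complete separation is the most extreme result possible, so at these sizes no result can print below 0.05 under either form.

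**3. Ties at the top (100% reduction), 10 v 10.**
- 6 or 10 tied: the direction is unchanged. True size is 3.1% and 3.3% with the correction, against 4.7% and 4.2% exact.
- 14 tied: some printed values fall slightly below the exact ones, but only above 0.09 (for example, exact 0.0975 prints as 0.0926 with the correction).
- 15 tied, all five untied values in one arm: the tied rank is 13, so W = 15 + 5 × 13 = 80 against a mean of 105. V = (100/12)(21 − 3360/380) = 101.3 and z = 24.5/10.07 = 2.434. Printed p = 0.025; exact p = 2 × C(15,5)/184,756 = 6,006/184,756 = 0.0325.
- 16 tied, all four untied values in one arm: the tied rank is 12.5, so W = 10 + 6 × 12.5 = 85 and the distance from the mean is 20. V = (100/12)(21 − 4080/380) = 85.5 and √V = 9.248. z = 19.5/9.248 = 2.109 prints 0.0485; without the correction, 20/9.248 = 2.163 prints 0.0435. Exact p = 2 × C(16,6)/184,756 = 16,016/184,756 = 0.087. The approximation's true size is then 8.7%, and the exact test cannot reach 0.05.

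**The case against.** The strongest case against is that nothing is decided by these p-values. The protocol describes an exploratory study ("no formal sample size calculation will be conducted"), section 16.2 says "no formal statistical test will be conducted", and the SAP sets no alpha for group comparisons. A descriptive 0.060 in place of 0.043, unadjusted across 12 visits, changes no rule. That stands, and it limits the harm. It does not justify printing a less accurate p-value when the accurate one costs nothing.

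A reader might also infer more than the documents support:

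- **That every rank sum p-value is too large.** This fails under very heavy ties, as the cases with 15 and 16 tied values show. The direction holds for no or moderate ties in the range of small p-values.
- **That the plan loses a definite amount of power.** A power comparison on normal data would not describe this plan. Such data would mostly pass the Shapiro-Wilk check and go to the t-test, if the check is read as choosing between the tests (the SAP does not spell the rule out).
- **That the Wilcoxon signed rank test has the same fault.** The SAP prescribes no approximation for it.
- **That strata too small for the approximation will occur.** Their sizes are unknown. At 3 v 3, 4 v 3 or 7 v 2 the exact test cannot reach 0.05 either.

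**Conclusion.** The point holds as a technical correction of limited consequence. At the trial's full size, and with few or moderate ties, the prescribed approximation overstates small p-values: 0.043 prints as 0.055 to 0.060, and true size is 2.9% to 3.5% instead of 4.3%. The relative error is larger in small strata, where a complete separation can be printed as unremarkable. With about 15 or more of 20 values tied, the error can turn anti-conservative. Neither direction can be relied on as a safeguard.

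The conclusion rests on the assumed form of the approximation (shown with and without the continuity correction), on two-sided 0.05 as a reference level, and on illustrative stratum sizes and tie patterns. What is at stake is the accuracy of descriptive p-values, not a missed decision.

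**What to change.** In SAP section 11, replace the sentence on the t-approximation with: *Wilcoxon rank sum p-values are exact (permutation distribution conditional on observed ties).* Apply it wherever a rank sum p-value is kept; if the sponsor drops the group p-values to match the protocol, the point falls away. The cost is one SAP sentence and an exact-test request in the analysis program. It needs no new data and no design change, and computing time is negligible at this sample size.
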